3.4 Examination of Subject Subsets

Additional analyses will be performed in subgroups of patients, including patients under the age of 22, patients with a baseline $K_{\max} \geq 47$, and patients with and without pre-procedure corneal scars. Results in male vs. female patients and different ethnicities may also be evaluated.

3.5 Multiple Comparisons

No multiplicity adjustments to control the Type I error rate will be considered.

3.6 Missing Data and Outliers

By definition of the EAS, there are no missing data for the primary endpoint. Missing data will not be imputed for any analysis. If a patient in the EAS has missing data for a secondary endpoint, they will not be included in the analysis of the secondary endpoint.

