1.1 Study Design

Approximately 3,000 eligible subjects presenting with asymmetric corneas will be enrolled at 21 clinical sites.

The planned primary effectiveness analysis will be based on 6-month post-procedure assessments. Subjects will be assessed post-procedure day 1, at 3 months and at 6 months. Visual acuity measurements and full ocular assessments (manifest refraction with CDVA, UCVA, slit lamp biomicroscopy including a rating of corneal haze, pachymetry, Pentacam corneal tomography, IOP) will be performed during that period.

According to the protocol, Optional 1 week, 1-2 month, 12-month, 24-month, and 36-month assessments will also be performed, at the discretion of the physician. The 1-2 month visit may occur if the subject experiences changes in refractive error, and requires a new prescription for spectacles or contact lenses.

In order to provide 12-month data to FDA for Phase 3 planning, sites were instructed to contact patients to request a 12-month assessment. In these cases, patients may have a 6-month visit that suggests they completed study, yet still return for the 12-month assessment. Not all patients that completed study at the 6-month visit will return for a 12-month assessment.

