2. DATA

The protocol states that patients complete study at Month 6, and subsequent visits are optional. In planning for the FDA meeting, sites have been instructed to request the Month 12 visit.

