3.2.3 Efficacy Analysis Set

The efficacy analysis set (EAS) population consists of all patients diagnosed with keratoconus, who do not have prior CK treatment, who do not have a prior corneal crosslinking procedure, and removed contact lenses per protocol as indicated on the CRF. Furthermore, patients must have a measure of change from baseline in at least one of the three efficacy endpoints. Analysis of efficacy endpoints will use the EAS. All EAS analyses will be performed by the treatment received as recorded on the CRF.

If the patient's diagnosis per-randomization does not correspond to the diagnosis captured on the medical history page or the diagnosis captured in the procedure page, that patient will be excluded from the EAS.

Determination of the efficacy analysis set may include utilization of patient lists provided by CXL if the criteria set for the EAS can't be directly determined from the CRF data.

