5.1 Primary Efficacy Endpoint

The primary measure of efficacy is the mean change from baseline in LogMAR of Corrected Distance Visual Acuity (CDVA) in the Primary Eye at Month 12 for each treatment group. As supportive analysis to the primary endpoint, the mean change from baseline and treatment differences will be estimated at Month 3 and Month 6.

Separately for each timepoint, analysis of variance (ANOVA) will be used to obtain point estimates and CIs for the change from baseline in LogMAR CDVA for each group. ANOVA will also be used to obtain point estimates and CIs for all pairwise comparisons between the treatment arms. P-values may be provided for descriptive purposes only.

As a sensitivity analysis, separate point estimates and confidence intervals for treatment differences based on a two-sample t-tests for each pairwise comparison will be performed without assuming equal variances. Satterthwaite approximation for degrees of freedom will be used.

Other sensitivity analysis such as mixed models repeated measures to account for the longitudinal nature of the data may be considered in an ad hoc manner.

The primary analysis will be repeated for the Fellow eye.

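### SAP 3.6 says no primary-endpoint data can be missing from the efficacy analysis set; Month 12 CDVA can be, so the primary estimates are observed-case and should be labelled so

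*SAP*

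**What the plan says.** SAP 3.6 makes two statements that bear on the primary endpoint: "By definition of the EAS, there are no missing data for the primary endpoint", and "Missing data will not be imputed for any analysis". It then says that a patient lacking a secondary endpoint is left out of that endpoint's analysis. It says nothing parallel for the primary endpoint, because on its premise the case cannot arise.

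SAP 3.2.3 defines the EAS as keratoconus patients with several exclusions, among them patients with earlier treatment (the set is limited to those "who do not have a prior corneal crosslinking procedure"). Its only data requirement is that "patients must have a measure of change from baseline in at least one of the three efficacy endpoints".

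SAP 5.1 sets the primary measure as the "mean change from baseline in LogMAR of Corrected Distance Visual Acuity (CDVA) in the Primary Eye at Month 12" for each treatment group, estimated by ANOVA separately at each timepoint. On longitudinal modelling it says only: "Other sensitivity analysis such as mixed models repeated measures to account for the longitudinal nature of the data may be considered".

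On attendance, SAP 2 records: "The protocol states that patients complete study at Month 6, and subsequent visits are optional". SAP 1.1 adds: "Not all patients that completed study at the 6-month visit will return for a 12-month assessment". SAP 1.4 limits efficacy to patients who have been in the study long enough to be eligible for a Month 12 visit.

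**The concern.** The sentence in 3.6 stands where the SAP should say what happens to a patient without the primary measurement. If it were true, no missing-data plan would be needed. If it is false, the primary estimates come from whichever patients returned at Month 12, and the SAP neither says so nor commits to any check on the consequences.

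No error rate is at stake, because SAP 3.2.3.1 rules out hypothesis testing. What is at stake is the purpose given there: estimating the Month 12 treatment effect in the population anticipated for Phase 3. If returning at Month 12, or being retreated before it, is related to outcome, those means and intervals are off target.

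**Working it through.** **Step 1: does the EAS rule guarantee the primary endpoint?**

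| Element | EAS rule (SAP 3.2.3) | Primary measure (SAP 5.1) |
|---|---|---|
| Endpoint | any one of CDVA, UCVA, Kmax | CDVA |
| Visit | none named | Month 12 |
| Eye | none named | Primary Eye |

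A patient whose only change value is Kmax at Month 3 meets the data rule and has no Month 12 CDVA. One such case refutes a claim made by definition.

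The gap is general. Three endpoints at three visits (Months 3, 6 and 12) give nine cells, each observed or missing.
- Patterns with at least one value: 2⁹ − 1 = 511.
- Of these, patterns without Month 12 CDVA: 2⁸ − 1 = 255.
- Patterns with no CDVA at any visit: 2⁶ − 1 = 63.

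These are counts of possible patterns, not expected proportions of patients. The 63 show that the sentence also fails if the primary endpoint is read as Month 6 CDVA (the protocol's timepoint) or as CDVA at any visit.

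**Step 2: does another section close the gap?** SAP 1.4 asks for enough time in the study to be eligible for Month 12, which is not attendance. SAP 1.1 and 2 say that attendance is optional and will be incomplete. SAP 5 lists Month 12 among the required visits, but its last sentence treats it as an optional visit that is kept. That keeps Month 12 in the analysis; it does not make the data complete.

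**Step 3: what estimate results?** With no imputation and one ANOVA per visit, a patient without Month 12 CDVA contributes nothing to the Month 12 estimate. The estimate is therefore observed-case.

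**Step 4: size.** For an arm with fraction missing *f*, the full mean is (1 − *f*) × observed mean + *f* × missing mean. Hence

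bias = observed mean − full mean = *f* × (observed mean − missing mean).

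The documents give neither *f* nor the gap, so both are assumed here:

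| Fraction missing | Gap 0.05 logMAR | Gap 0.10 logMAR |
|---|---|---|
| 20% | 0.01 | 0.02 |
| 40% | 0.02 | 0.04 |
| 60% | 0.03 | 0.06 |

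The sign can go either way. If data are missing completely at random, the expected gap and the bias are zero.

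A contrast between arms is biased when the product *f* × gap differs between them. Equal fractions missing do not protect it: with 40% missing in both arms and gaps of 0.05 and 0.10, the arm biases are 0.02 and 0.04, and the contrast is off by 0.02.

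For scale, the SAP 1.3.1 formula with usual chart lines (assumed) gives log₁₀(25/20) = 0.097, log₁₀(30/25) = 0.079 and log₁₀(40/30) = 0.125. The top of the table, 0.06, is roughly half to three quarters of one chart step.

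**Step 5: what would the planned outputs reveal?** SAP 3.1 includes the number of observations by treatment, so EAS size minus the Month 12 CDVA count gives the number missing per arm. Listing 2 identifies retreated patients. Disposition (SAP 4.1) counts completion at Month 6 and takes discontinuation from the end-of-study page, so a Month 6 completer who does not return would ordinarily appear as a completer. The number missing can be recovered; the reasons are not tabulated.

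**The case against.** The strongest reply is that the SAP hides nothing. SAP 1.1 says openly that some patients will not return, SAP 3.1 puts the number of observations in the summaries, and the handling follows from 3.6 and 5.1 taken together. The work is descriptive, for programme development, and 5.1 already names a repeated-measures model. Much of this stands. A reader might infer from 3.6 that the Month 12 results will be passed off as complete. The documents do not support that: non-return is disclosed, and no planned table is described as complete-data. What remains is a false statement, a missing label and no committed sensitivity analysis.

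Two other strong readings also fail.
- A reader might infer that the EAS will include patients not yet due for Month 12, because 3.2.3 omits the eligibility condition. SAP 1.4 confines efficacy to patients eligible for that visit, and read together the two sections probably exclude the rest. The omission is a drafting gap.
- A reader might infer that the estimates will be too favourable because poor responders are retreated and lose their Month 12 value. SAP 2.3 says only that the investigator may elect a repeat after the Month 6 assessment. It gives no reason or timing, and a repeat after Month 12 would lose nothing.

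How a retreated eye is handled is nevertheless not stated. The exclusion of earlier cross-linking and the second patient number (SAP 2.3) suggest that second-course values stay out. But 2.3 also maps all data to one patient, and SAP 3.8.2 sets each eye's baseline by its procedure, with no rule for an eye that has two. The protocol text on exit and re-enrolment (Protocol 5.4) is in a version headed 04.1, whereas the SAP cites 4.3, so it cannot settle the matter.

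**Conclusion.** The concern holds. The 3.6 sentence contradicts 3.2.3, 5.1, 1.1 and 2, and no reasonable reading of the primary endpoint rescues it. As a result the primary Month 12 estimates are observed-case without being labelled so.

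The size and direction of any bias cannot be found from the documents. The 0.01–0.06 logMAR range rests wholly on the assumed 20–60% missing and gap of 0.05–0.10; it is an illustration, not a forecast. This should be fixed before the analysis is run. It does not invalidate the exercise, because nothing is tested and the shortfall can be recovered from the reported counts.

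**What to change.** 1. **SAP 3.6.** Replace the sentence with: *Month 12 CDVA change may be missing for patients in the EAS; ANOVA estimates at each visit use patients observed at that visit and are labelled observed-case.*
2. **SAP 5.1.** Keep the ANOVA. Make the repeated-measures model a committed sensitivity analysis using Months 3, 6 and 12 in all EAS patients with any post-baseline CDVA. SAP 3.3 needs amending only if baseline CDVA enters as a covariate.
3. **SAP 4.1.** Report by arm the numbers eligible for Month 12, retreated before it, and with CDVA observed at it.
4. **SAP 3.2.3.** Repeat the Month 12 eligibility condition from 1.4. State that values after a repeat procedure on an eye are not used as that eye's first-course Month 12 values; the paired-number list in 2.3 can identify them.

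The cost is SAP wording and modest programming on data already collected. The downside of item 2 is that the model assumes missingness is explained by the observed visits. If return depends on the Month 12 outcome itself, bias can remain. A shift analysis for the missing Month 12 values would address that. It is optional, and it would require relaxing the no-imputation sentence in 3.6.

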3.7 Study Eye

For the efficacy endpoints collected on both eyes, only the “worse” eye at randomization will be designated as the study eye and used as the primary eye in the efficacy analyses. The worse eye will be defined as the eye with the lowest CDVA at randomization. If both eyes have the same CDVA, then the eye with the greater K_{\max} will be chosen. If both eyes have the same K_{\max} and same CDVA, then the right eye will be designated as the study eye. If only one eye initially receives treatment, then that eye will be designated as the study eye and used in the analyses. The study eye will be labeled as the “Primary Eye” and non-study eye will be labeled as the “Fellow Eye” in the Tables and Listings.

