5.4 TIMING OF STUDY ASSESSMENTS

All procedures will be performed according to the following schedule unless otherwise specified. When assessments are scheduled, subjects will be instructed to remove contact lenses prior to screening – 2 weeks prior for rigid/gas permeable contact lenses and 3 days prior for soft or scleral lenses – unless subject has no suitable vision correction option.

Pre-Procedure:

Assessments:

- UCVA
- Manifest refraction
- CDVA
- Pentacam corneal tomography
- Pachymetry by ultrasound or other scanning device such as Pentacam
- Slit lamp examination
- Intraocular pressure (IOP)

- Dilated fundus exam (or documented dilated fundus exam by another provider within 1 year)
- Medial history
- Contact lens history
- History of previous eye surgeries

Optional Assessments:

- Quality of life and/or comfort survey questions such as VFQ-25.
- Optional assessments including corneal wavefront, optical coherence tomography (OCT), Brillouin microscopy, iTrace wavefront aberrometry/topography, Orbscan corneal topography, tomography, contrast sensitivity testing, or other non-invasive diagnostic tools that may be available to an investigator.
- Previous ophthalmic history such as:
 - Previous old eyeglass prescriptions & topographic maps may be requested and documented.
 - UCVA within the past 3 months (if evaluation was performed at the same clinic as that involved in this study);
 - CDVA within the past 3 months (if evaluation was performed at the same clinic as that involved in this study);
 - Manifest refraction within the past 3 months (if evaluation was performed at the same clinic as that involved in this study).

Day 1 Post-Procedure:

Assessments:

- UCVA
- Slit lamp examination

Optional Assessments:

- CDVA
- Manifest Refraction
- IOP
- Pachymetry
- Optional assessments including Pentacam corneal tomography, corneal wavefront, optical coherence tomography (OCT), Brillouin microscopy, iTrace wavefront aberrometry/topography, Orbscan corneal topography, tomography, contrast sensitivity testing, or other non-invasive diagnostic tools that may be available to an investigator.

Optional Visit Days 2-10 (If Post-Procedure Day 1 shows incomplete epithelium healing):

Assessments:

- UCVA
- Slit lamp exam
- IOP

Optional Assessments:

- Manifest refraction and CDVA
- Pachymetry

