2.1 Filtering

Data to be presented in the efficacy analysis are limited to a subset of patients as defined in Section 3.2.3. Filtering will only be done on efficacy data. Baseline and safety data will include all patients randomized and treated as of the data lock date.

Due to database limitations, randomization date is assumed to be the date of the first procedure as determined by the visit date for the Procedure Visit.

Some patients will have longer follow-up data than others. Filtering will not attempt to exclude data from beyond the Month 12 visit. All safety data will be used, but efficacy data beyond Month 12 CRF page will not be analyzed.

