3.8.2 Definition of Study Baseline

Study baseline is defined as the last observation obtained on or prior to the start of the procedure on the first eye on Study Day 1.

Change from baseline is defined as post-baseline assessment minus baseline assessment. Baseline value will not be carried forward to impute the post-baseline values.

For efficacy measures performed on individual eyes, baseline will be determined for each eye separately based on the date of the procedure on each particular eye.

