8. APPENDICES

8.1 Appendix A: Schedule of Assessments

	Pre-Procedure	Post-Op Day 1	Optional Post-Op Days 2-10	Optional Post-Op Month 1-2	Post-Op Month 3 (60-120 Days)	Post-Op Month 6	Optional Post-Op 1 Year	Optional Post-Op 2 Year	Optional Post-Op 3 Year
Informed Consent	X								
Demographics	X								
Medical History/Concomitant Medications	X			X ³	X	X	X	X	X
Contact Lens History	X			X ³	X	X	X	X	X
History of Prior Eye Surgery	X								
Slit Lamp Exam	X	X	X	X	X	X	X	X	X
Fundus Exam	X ¹								
Intraocular Pressure (IOP)	X	X ³	X	X	X	X	X	X	X
Uncorrected Visual Acuity (UCVA)	X	X	X	X	X	X	X	X	X
Corrected Distance Visual Acuity (CDVA)	X	X ³	X ³	X ³	X	X	X	X	X
Manifest Refraction	X	X ³	X ³	X ³	X	X	X	X	X
Pachymetry	X ²	X ³	X ³	X	X ²	X	X	X	X
Pentacam Corneal Topography/Tomography	X	X ³	X ³	X	X	X	X	X	X
Quality of Life Survey	X ³				X ³	X ³	X ³	X ³	X ³
Prior Eyeglass Prescriptions, UCVA, CDVA, and Topographic Maps	X ³								
Other Optional Assessments	X ⁴	X ⁴	X ⁴	X ⁴	X ⁴	X ⁴	X ⁴	X ⁴	X ⁴

¹Or documented dilated fundus exam by another provider

²By ultrasound or other scanning device such as Pentacam

³Optional assessment procedures

⁴Other Assessments include corneal wavefront, optical coherence tomography (OCT), Brillouin microscopy, iTrace wavefront aberrometry/topography, Orbscan corneal topography, tomography, contrast sensitivity testing, or other non-invasive diagnostic tools that may be available to an investigator.

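### In initially bilateral patients the Primary Eye is chosen on what is in practice its own baseline CDVA, so no SAP output of within-group CDVA change that includes them is free of regression to the mean

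*SAP*

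**What the plan says.** SAP 3.7 designates one study eye per patient. Where both eyes are treated initially, "The worse eye will be defined as the eye with the lowest CDVA at randomization"; ties on CDVA go to the eye with the greater Kmax. Where only one eye is treated initially, that eye is the study eye and no CDVA comparison is made.

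Three other places fix which reading that is:

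- SAP 2.1: "randomization date is assumed to be the date of the first procedure as determined by the visit date for the Procedure Visit".
- SAP 3.8.2: "Study baseline is defined as the last observation obtained on or prior to the start of the procedure on the first eye", and for eye-level measures "baseline will be determined for each eye separately based on the date of the procedure on each particular eye".
- Protocol 5.4 and the schedules of assessments require one pre-procedure CDVA. Earlier values appear only as optional history (the row "Prior Eyeglass Prescriptions, UCVA, CDVA, and Topographic Maps" in SAP Appendix A). Protocol 8.0 defines baseline as the pre-procedure visit.

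SAP 5.1 then states: "The primary measure of efficacy is the mean change from baseline in LogMAR of Corrected Distance Visual Acuity (CDVA) in the Primary Eye", per treatment group at Month 12, with Months 3 and 6 as support. SAP 5 repeats the analysis for the Fellow Eye as a separate set of results. SAP 3.3 allows no covariates. SAP 1.4 and Protocol 8.1 say that all treated eyes enter the efficacy analysis, but SAP 5 and the table list in Appendix B specify no output that combines the two eyes. SAP 1.6 does not list the use of a single worse eye as a change from the protocol.

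**The concern.** An eye chosen because it read worse than its fellow tends to have been read with unfavourable error on that occasion. If the same reading is then subtracted as baseline, the error is absent at follow-up and the eye appears to improve with no true change. The Fellow Eye, being the better of the pair on the same reading, appears to worsen by the same amount. The Fellow Eye repeat is therefore not a clean check on the Primary Eye result.

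The shift does not shrink with sample size, and the planned 95% confidence intervals do not reflect it.

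At stake is the use of these estimates. The SAP Introduction says that the interim data will help design Phase 3, and SAP 3.2.3.1 speaks of estimating a Month 12 treatment effect. All three arms receive cross-linking, so arm differences compare only UVA settings. Any reading of the effect of cross-linking itself from this study would have to come from within-group change. The SAP does not say which quantity will be carried forward.

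**Working it through.** The documents state no figure on this point, so there is none to reproduce.

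**Inputs, all assumed.** `se` is the SD of a single CDVA reading in logMAR. `sw` is the within-patient SD of true CDVA per eye. True change is zero. Reading errors are independent between eyes and visits.

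**Formula.** Let D be the difference between the two eyes' baseline readings. Its variance is `2(sw² + se²)`, so `E|D| = 2·sqrt((sw² + se²)/π)`. The share of D due to error is `se²/(sw² + se²)`, and half of it falls on the worse eye. The spurious change in the Primary Eye is therefore

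`shift = ½ · E|D| · se²/(sw² + se²) = se² / sqrt(π(sw² + se²))`

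toward improvement, and equal and opposite in the Fellow Eye. Over all primary eyes it is multiplied by the initially bilateral share.

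| se | sw | Shift in bilateral patients | All primary eyes at 25% / 50% / 75% bilateral |
|---|---|---|---|
| 0.05 | 0.30 | 0.0025/√(π × 0.0925) = 0.0046 | 0.001 / 0.002 / 0.003 |
| 0.08 | 0.15 | 0.0064/√(π × 0.0289) = 0.0212 | 0.005 / 0.011 / 0.016 |
| 0.12 | 0.10 | 0.0144/√(π × 0.0244) = 0.0520 | 0.013 / 0.026 / 0.039 |

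At an assumed 0.02 logMAR per letter, the bilateral range is 0.2 to 2.6 letters. The middle row at 50% bilateral is about half a letter. No row is preferred.

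**Simulation check** (2,000,000 patients per run, three arms, 50% bilateral, Kmax tie-break as in SAP 3.7, zero true change). For the middle row:

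- Bilateral Primary Eye: -0.0213, -0.0212 and -0.0214 at Months 3, 6 and 12.
- Initially treated Fellow Eye: +0.0211.
- Unilateral patients: 0.000.
- Differences between arms: within 0.0006, which is simulation noise.
- All initially treated eyes pooled: -0.0001.

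Rounding readings to 0.1 logMAR gave -0.0059, -0.0224 and -0.0515 for the three rows, so coarse acuity steps do not remove the effect. Kmax change moved by 0.008 to 0.014 D in size, only through the tie-break (assumed Kmax reading SD 0.7 D, per-eye SD 3.5 D).

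**How far pooling the eyes helps.** Suppose a share m of initially treated fellow eyes lacks CDVA at a visit where the primary eye has it. With equal weight per eye, the remaining fraction of the bias in bilateral patients is `[1 - (1 - m)] / [1 + (1 - m)] = m/(2 - m)`, which is 5%, 11% and 18% at m = 10%, 20% and 30%. An exchangeable or random-intercept model gives single-eye patients relatively more weight. The fraction becomes `m / (m + 2(1 - m)/(1 + ρ))`, where ρ is the between-eye correlation of change. At an assumed ρ of 0.5 this is 8%, 16% and 24%.

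**The case against.** The strongest reply is that little depends on this. SAP 3.2.3.1 says that no hypotheses are tested and that the estimates are descriptive. The treatment effect it mentions could equally mean the arm contrasts, since "ANOVA will also be used to obtain point estimates and CIs for all pairwise comparisons between the treatment arms", and those are unbiased in expectation. If Phase 3 relied on a difference between arms, or kept the same worse-eye rule, the shift would not mislead it. The size is wholly assumed and may be negligible. The top of the range needs reading error larger than the true per-eye SD. All of this stands, and it keeps the point minor.

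A second reply is that the bias can largely be undone from planned tables: an average of the Primary and Fellow means, weighted by the number of eyes, cancels it where both eyes have data. That is true of the point estimate. It gives no standard error that allows for two eyes from one patient, and the SAP does not tell the reader to do it.

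A third is that SAP 1.4 and Protocol 8.1 already promise an analysis of all treated eyes. Run as one pooled mean, that would be free of this shift. But no such output is specified, SAP 5 splits the eyes, and the SAP governs where the two documents differ. The claim is therefore about SAP outputs, not about every analysis the protocol might allow.

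A reader might infer that the comparison of UVA groups is compromised, or that any improvement seen must be an artefact. The documents support neither. The rule acts alike in all randomized arms, and nothing in the plan fixes the size of the shift relative to a true change.

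**Conclusion.** The point holds for within-group change in LogMAR CDVA, Primary and Fellow Eye, including the subgroup tables, to the extent that initially bilateral patients are in the efficacy set. The assumed size is 0.005 to 0.052 logMAR in those patients, and 0.011 over all primary eyes in the middle case at 50% bilateral.

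It rests on these assumptions:

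- The selecting and baseline readings coincide. This is an inference from the definitions and the single mandatory reading; an extra pre-procedure CDVA could break it.
- Lowest CDVA means poorest acuity, as the word worse implies. Applied to the LogMAR value, the rule would pick the better eye and the sign would reverse.
- Equal size at Months 3, 6 and 12 requires reading errors independent between visits. Error that persists would make the shift smaller.

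Outside the claim: initially unilateral patients and later-treated fellow eyes with their own baseline get no bias from this rule, and Kmax change is largely unaffected. UCVA change is affected only so far as CDVA and UCVA errors at the same visit are correlated.

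This is a minor, inexpensive improvement to a descriptive analysis. It matters if within-group change is taken into Phase 3 planning.

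**What to change.** Keep the Primary Eye estimate and make two additions.

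1. Add to SAP 5.1 as supportive: *Mean change from baseline in LogMAR CDVA per group will also be estimated over all initially treated EAS eyes (first course only), with equal weight per eye (GEE with independence working correlation, patient as cluster, robust standard errors), and reported beside the Primary Eye estimate.* The working correlation should be named, because an exchangeable or random-intercept model leaves more of the bias when fellow-eye data are missing.

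2. Footnote the Primary Eye and Fellow Eye within-group CDVA tables (4.1.1 to 4.3.2) as subject to regression to the mean in initially bilateral patients, and note possible carry-over to the UCVA tables (5.x). Report the initially bilateral share within the EAS. Take it from the treated-eye record for initial treatment (OD, OS or OU, as in SAP 4.1). The patient number will not serve, because under SAP 2.3 a patient treated in one eye only also has a single number. Nor will the SAP 4.3 count, which feeds Table 3 on the Safety Analysis Set.

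The cost is one supportive analysis on data already collected, one count and a footnote. The pooled estimate describes all initially treated eyes rather than worse eyes. It does not address how the treated eye was chosen in unilateral patients, or incomplete return at Month 12.
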